#### 2. Heart rate (HR)

Heart rate is obtained from the ECG (EG) data where available. If 180 day ECG data is not available, heart rate from the vitals data for the visit or from the medical record close to the visit is used. For participants who have two baseline ECG measurements average is taken prior to calculating change from baseline.

a) HR change from baseline to 180 days = EG.ECGHR (where VCISITID=10) – EG.EGHR (where VISITID=50) if 180 day ECG is not missing.

or

= EG.ECGHR (where VISITID=10)-VS.PULSE (where VISITID=50) if 180 day ECG is missing.

b) HR at 180 days= EG.ECGHR (where VISITID=50) if 180 day ECG is not missing  
or

=VS.PULSE (where=VISITID=50) if 180 day ECG is missing

Note: missing HR at 180 days will be imputed using MI technique per (Section 12.5)

c) Proportion of participants with heart rate < 70 bpm at 180 days

If HR at 180 days (see b) above) is < 70bpm (but not missing) then HR less than 70 bpm=1; else HR less than 70 bpm=0.

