## **9.2 Secondary Analyses**

### **1. Heart Rate Assessments**

- a. Change in heart rate from baseline to 180 days will be compared across randomization groups. Change will be calculated as follows: (Baseline heart rate – 180 day heart rate). Comparisons across randomization groups will be performed using a linear model with adjustment for baseline heart rate and beta-blocker use. Randomization groups will be included in the regression model as main effect.

---

 Baseline beta-blocker use will be coded as a “0/1” variable with participants who received beta-blocker coded as “1” and those who did not receive beta-blocker as “0”.

 All change from baseline results presented are calculated similarly.

Heart rate is expected to be lower in the ivabradine arm than the usual care arm.  
Thus, change from baseline is expected to be higher in the ivabradine arm.

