### **13.5 Handling of Missing Data**

All efforts will be made to make sure all data needed for the analyses outlined in the SAP are complete. However, it is possible that some data will be missing. Missing data is a common problem in clinical research. It reduces statistical power (the probability that the test will reject the null hypothesis when it is false) and results in biased parameter estimates (Kang, 2013). Outcomes for participants who do not provide data during the 180 day visit will be imputed as failures. Missing heart rate, PGA and KCCQ values will be imputed for the final (180 day) visit using multiple imputation technique if more than 10% of the measures are missing.

It is expected that missing 180 day visit values constitute > 10% of the secondary endpoints (Heart rate, KCCQ and PGA). Thus, multiple imputation (MI) will be performed and presented for the ITT and Treated populations, respectively.

Imputation will be conducted using PROC MI and imputed data analyzed with PROC MIANALYZE in SAS 9.4.

The following variables shall be used in the imputation:

AGE, SEX, RACE, ETHNICITY, WEIGHT, NYHA class, LVEF, and baseline value of the imputed variable) – For NYHA class, WEIGHT and LVEF, baseline values will be used.

RACE shall be recoded to: White, Black and Others (combining American Indian, other, and mixed - as they are of very low frequency)

Results of the imputation shall be presented as the primary result of the secondary endpoints. A total of 25 imputations will be conducted for each imputed value.

Sensitivity analyses will be conducted by analyzing these endpoints with and without imputation.

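### Multiple imputation for day-180 heart rate, KCCQ and PGA omits randomised arm and so shrinks real differences; for heart rate below 70 bpm the non-imputed run cannot show this, because it codes missing as 0

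*SAP*

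**What the plan says.** **Imputation (SAP 13.5).** On missing data: "It is expected that missing 180 day visit values constitute > 10% of the secondary endpoints". Values are imputed with PROC MI and combined with PROC MIANALYZE; "A total of 25 imputations will be conducted for each imputed value". On status: "Results of the imputation shall be presented as the primary result of the secondary endpoints". The variables are "AGE, SEX, RACE, ETHNICITY, WEIGHT, NYHA class, LVEF, and baseline value of the imputed variable". Randomised arm and baseline beta-blocker use are not listed. Results are to be shown for the ITT and Treated populations; nothing says that imputation is done within arm. A second run is required: "Sensitivity analyses will be conducted by analyzing these endpoints with and without imputation".

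**Analysis (SAP 9.2).** Change in heart rate (1a) uses a "linear model with adjustment for baseline heart rate and beta-blocker use", and "Randomization groups will be included in the regression model as main effect". Day-180 heart rate (1b), KCCQ and PGA have models of the same form. For heart rate below 70 bpm (1c), only a chi-square test is named, or Fisher's exact test if events are rare.

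**Derivation of 1c (SAP Appendix 1, Heart rate, item c).** It takes the day-180 heart rate of item b, which is to be multiply imputed. If that value "is < 70bpm (but not missing) then HR less than 70 bpm=1; else HR less than 70 bpm=0".

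**Neighbouring rules.** SAP 13.2 uses non-missing denominators by default. In Appendix 1, maximum ivabradine dose (Ivabradine use, item d) and beta-blocker target dose (Beta-blocker use, item b) assign 0 only when the dose is recorded. Protocol 10.4 mentions multiple imputation for 1a, 1b, KCCQ and PGA without listing variables, and gives no analysis for 1c.

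**The concern.** An imputation model should contain every variable in the analysis model, above all the one whose effect is being estimated. If arm is left out, a participant with no day-180 value is given a value typical of both arms together, and the completed data understate any real difference. Here that affects the result labelled primary for the secondary endpoints.

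For 1c the planned cross-check fails too. The words in brackets in item 2c stop a missing value from becoming 1, but the unguarded 'else' then makes it 0. In imputed data sets no value is missing and the branch does nothing. In the non-imputed run it turns every missing participant into a non-responder.

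**Working it through.** **Inputs.** From the documents: 104 enrolled (SAP 2.3), taken as 52 per arm; more than 10% missing, so at least 11 participants (0.10 × 104 = 10.4); 25 imputations; a 5-point KCCQ difference (Protocol 10.2). The plan's KCCQ power reproduces closely: 207 per arm, SD 16 and 5 points give 0.889 against the stated 90% or so. The documents give no heart-rate SD, no rate below 70 bpm and no missingness by arm, so the values below are assumed.

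**Step 1: imputation without arm.** Let the arm means differ by δ, let m1 and m0 be the missing fractions, and let data be missing completely at random within arm. Baseline covariates are balanced by randomisation, so imputed values in both arms centre on the pooled observed mean. The completed-data difference is

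δ × 2(1 − m1)(1 − m0) / [(1 − m1) + (1 − m0)],

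which is δ(1 − m) when m1 = m0 = m.

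- 8 bpm: 8 × 0.89 = 7.1; 8 × 0.80 = 6.4; 8 × 0.70 = 5.6.
- 5 KCCQ points: 4.45, 4.0 and 3.5.
- Unequal missingness, 8 bpm: 6.8 at 10% v 20%; 6.6 at 10% v 25%.
- δ = 0 gives 0, so no difference is created.

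**Step 2: item 2c without imputation.** Each arm's proportion p becomes p(1 − m), so the reported difference is p1(1 − m1) − p0(1 − m0).

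- Equal missingness: the true difference times (1 − m), the same factor as in step 1.
- No true effect, missingness 10% v 25%: 0.15p, or 4.5 points at p = 30% and 7.5 at p = 50%. At 10% v 20% it is 3.0 to 5.0 points.

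**Step 3: simulation.** 52 per arm, 1000 replicates per setting; day-180 means 76 and 68 bpm, SD 12, correlation 0.4 with baseline; 25 normal-regression imputations on baseline heart rate plus eight noise covariates standing for the rest of the list. True 1c difference: Φ((70 − 68)/12) − Φ((70 − 76)/12) = 0.566 − 0.309 = 25.8 points (rounded from unrounded values). Monte Carlo standard error is at most 0.36 points.

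| Missing, both arms | 8 bpm effect, MI without arm | 1c, MI without arm | 1c, missing = 0 | 1c, observed only | 1c, MI with arm |
|---|---|---|---|---|---|
| 11% | 7.2 | 23.0 | 23.1 | 25.9 | 25.6 |
| 20% | 6.4 | 20.6 | 20.7 | 25.9 | 25.4 |
| 30% | 5.6 | 18.3 | 18.3 | 26.2 | 25.0 |

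With arm in the imputation model, the 8 bpm effect is returned as 8.0 to 8.1.

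Range for 1c at 20% missing (true; MI without arm; missing = 0; MI with arm):

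- 4 bpm effect: 12.5; 10.0; 10.0; 12.3.
- 12 bpm effect: 38.3; 30.4; 30.3; 37.3.
- SD 10: 30.5; 24.1; 24.2; 29.6.
- SD 15: 20.8; 16.6; 16.7; 20.3.

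A separate simulation with other inputs (control mean 78 bpm, residual SD 12, 8 bpm effect, only baseline heart rate with or without arm, 1500 runs) gave the same pattern. At 20% missing, power for a pooled 1c risk difference was 0.47 without arm and 0.66 with it.

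**The case against.** **The non-imputed run is a safeguard.** For 1a, 1b, KCCQ and PGA this stands. That run fits a model containing arm to observed data, so the shrinkage could be seen by comparison. SAP 5.2 and Appendix 2 also plan a mixed model for heart rate that contains treatment. A reader might infer that both versions of every secondary endpoint are biased alike. The documents support that only for 1c, and only when missingness is about equal.

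**Coding missing as 0 may be intended.** SAP 13.5 says that day-180 outcomes not provided count as failures, 13.2 allows stated exceptions, and the any-initiation flag (Appendix 1, Ivabradine use, item c) also has a bare 'else'. This does not persuade. In 9.1 and 9.3, failure means no ivabradine use; the next sentence of 13.5 assigns heart rate to imputation; and a failure-coded run is not a run without imputation. The any-initiation flag is an ever-use variable, for which no record of receipt reasonably means 0.

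**A pooled 1c result can still be produced.** This stands. A reader might infer from the bare chi-square test that it cannot, but each arm's proportion has a standard error and a difference can be pooled. What is missing is detail. That imputation applies to 1c is itself read from item c's reference to item b together with 13.5; 1c is not named.

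**The size is modest.** This stands in part. At 11% missing the simulated 1c loss is 25.8 − 23.0 = 2.8 points, against a standard error near 9.4 points with 52 per arm, or about 0.3 standard errors. But the bias is systematic, grows with missingness and is avoidable.

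**Beta-blocker use is unquantified.** This stands. Eligibility asks for maximally tolerated beta-blockers or intolerance, so the variable may vary little.

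**Conclusion.** Wrong as written. The arm omission affects the result labelled primary for heart rate, KCCQ and PGA, and shrinks a real difference by about the missing fraction: just over a tenth at the level the SAP expects, and 20% or 30% at those assumed levels. The unguarded 'else' affects only the non-imputed 1c run, but removes that run's value as a check. It reproduces the same shrinkage under equal missingness and can show a false difference under unequal missingness.

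The factor (1 − m) rests on equal missingness, completely at random within arm. The bpm and percentage-point figures also rest on assumed means, SDs and rates.

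A reader might infer that the plan manufactures a benefit, or that the trial's primary endpoint is affected. Neither follows. Imputation without arm biases toward the null, and ivabradine use has its own explicit failure rule in SAP 9.1. How heart rate is treated after death is a separate estimand choice and not part of this point. The text reviewed includes Addendum 2 but no Addendum 1; if that changed the imputation list, the first part would need revisiting.

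**What to change.** 1. In SAP 13.5, add randomised arm to the imputation variables, or impute separately by arm. Add baseline beta-blocker use so that the imputation model holds all covariates of the analysis models. Re-run the 25 imputations for heart rate, KCCQ and PGA.
2. In Appendix 1, Heart rate, item c, assign 0 only when the day-180 heart rate is present and not below 70 bpm; otherwise leave the indicator missing. The non-imputed run then uses observed data and keeps the chi-square or Fisher test.
3. As a consequential clarification in 9.2, for the imputed 1c result: dichotomise at 70 bpm after imputation, estimate the risk difference and its standard error in each data set, and pool in PROC MIANALYZE.
4. Record this in a dated amendment that states its timing relative to unblinding. Addendum 2 already records a change made after database lock and unblinding, so a change made now should be labelled post hoc.

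Cost: two added variables, one derivation line, a short pooling rule and a re-run of the imputations and models. No new data are needed. Missing at random is still assumed. Under missing completely at random, the corrected imputation gives about the same estimate as the observed data, so the gain is removal of the shrinkage, not extra information.

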### 3. Kansas City Cardiomyopathy Questionnaire (KCCQ)

KCCQ change from baseline to 180 days is obtained from the KCCQ analysis (KCCQD) data created from the KCCQ survey using the KCCQ scoring algorithm.

KCCQ change= KCCQD.KCQOSBL –KCCQD.KCCQOSS (where VISITN=50)

Note: missing KCCQ values at 180 days will be imputed using MI technique per (Section 12.5)

### 4. Patient Global Assessment (PGA)

PGA change from baseline to 180 days is obtained from the PGA (PGA) data.

PGA change from baseline to 180 days= PGA. PGAMM (where VISITID=10) – PGA.PGAMM (Where VISITID=50)

Note: missing PGA values at 180 days will be imputed using MI technique per (Section 12.5)

### 5. Beta-blocker (BB) use

Beta-blocker use measures were obtained from the current medication (CM) data

Baseline BB use at baseline = CM.CMBB =1 where VISITID=10).

a) BB use at 180 days = CM.CMBB=1 (where VISITID=50)

b) Proportion on target dose at 180 days (doses were calculated based on Carvedilol equivalent basis).

If VISITN =50 and Carvedilol equivalent dose = 50 mg then on target dose=1 (yes); else if Carvedilol equivalent dose is not missing on target dose=0(no).

c) Proportion on 50 % of target dose (Carvedilol equivalent) at 180 days.

If Carvedilol equivalent dose is at least 25 mg then on 50% target dose=1; else if Carvedilol equivalent dose is not missing on 50% target dose =0.

d) Proportion of participants discontinuing (No beta-blocker use at 180 days in those who used it during an early visit)

e) Mean change in dose (Carvedilol equivalent)

Change in dose from baseline to 180 days (converted to Carvedilol equivalent dose) = CM.CMBBDS (where VISITID=10) – CM. CMBBDS (where VISITID=50)

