### 2.5.3 Tertiary endpoints

Tertiary endpoints are

- 1) Beta-blocker use at 180 days as assessed by the:
  - a) Proportion of participants on beta-blocker at 180 days
  - b) Proportion on target dose
  - c) Proportion discontinuing beta-blockers at 180 days and
  - d.) Mean change in beta-blocker dose from discharge to 180 days.
- 2). Ivabradine use at 180 days as assessed by the:
  - a) Proportion of appropriate participants with any initiation of ivabradine at 180 days
  - b) Proportion of appropriate participants at the maximum dose of ivabradine at 180 day.
  - c) Mean dose of ivabradine achieved at 180 days.
- 3). Tolerability of ivabradine and events of interest:
  - a) Symptomatic bradycardia
  - b) Symptomatic hypotension
  - c) Other symptoms leading to ivabradine discontinuation
- 4). Summary of barriers to acquisition of ivabradine

---

 Beta-blocker target dose is defined as participants who receive Carvedilol equivalent total daily dose of 50 mg

 Appropriate participants are defined as participants who have a sinus rhythm (participants excluding those with AF) and heart rate of  $\geq 70$  bpm. For participants missing 180 day ECG, results from the baseline ECG are used to determine appropriateness.

 Receiving ivabradine at any time point during the study.

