### **13.2 General Analysis Conventions/Rules**

All analyzed continuous variables will be summarized using descriptive statistics including number of observations, mean, standard deviation, minimum, 25th percentile, median, 75th percentile, and maximum. All analyzed categorical variables will be summarized using frequency counts and percentages. Percentages are calculated out of non-missing values unless stated otherwise. Comparisons of continuous (or discrete ordered) variables between randomization groups will generally be tested using the Wilcoxon rank sum test. For the secondary endpoint (change from baseline of the measures), analyses will be conducted using the general linear model approach. For comparisons over more than 2 time points, when appropriate, mixed effects models will be used to account for correlation within participant observations and assess time-by-treatment interactions (see Appendix 2 for details). Tests of binomial outcomes between randomization groups will generally be done with a Chi-square statistic. Tests of treatment effects will generally be 2-sided, with type I error = 0.05. Interaction tests will generally be done at the 0.10. Statistical significance is determined at a  $\leq$  0.05 alpha level.

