### Data Sources for Endpoints

#### 1. Ivabradine use

a) Ivabradine use (1/0) at 180 days comes from either the current medications data (CM) or the ivabradine usage data (DRG).

If CM.CMIVA=1 and VISITID=50 or DRG.DRIVA=1 and VISITID=50. If missing then it is imputed to 0. (Note: analysis will also be done without imputation).

b) Ivabradine dose change from baseline to 180 days

Ivabradine use and dose at baseline comes from the ivabradine initiation in hospital (EXH) data EXH.EXRECH (use) and EXH.EXLDH (dose) EXH.EXRECH (use) and EXH.EXLDH (dose) (VISITID=10) and ivabradine obtaining the first time (outpatient) (EX) EX.EXREC and EX.EXPDOS (VISITID=60 study wide to be merged in)

For other time points use the ivabradine usage data DRG.DRIVA (use) DRG.DRDSG (dose). Missing doses will be imputed to 0. (Note: analysis will also be done without imputation).

Dose change from baseline to 180 days = EXH.EXLDH, EX.EXDOS (VISITID=10)-DRG.DRDSG (where VISITID=50)

c) Proportion with any initiation

If participant received ivabradine at any time during the visits

If EXH.EXRECH=1 or EX.EXREC=1 or CM.CMIVA=1 or DRG.DRIVA=1 at any visit then ANYIVA=1 else ANYIVA=0; (Note: No imputation of missing ivabradine use occurs for this derivation)

d) Proportion on maximum dose at 180 days

Use ivabradine usage data

If DRG.DRSG =15 (mg) and VISITID=50 then on ivabradine maximum dose=1; else if DRG.DRSG not missing on ivabradine maximum dose=0.

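### SAP Appendix 1 codes beta-blocker target dose as exactly 50 mg carvedilol-equivalent, so any higher dose is counted as off target

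*SAP*

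**What the plan says.** The proportion on beta-blocker target dose at 180 days is a named tertiary endpoint in both documents (Protocol 10.4; SAP 2.5.3). SAP 9.3 item 1 compares it between arms with a Chi-square test.

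- **Definition in the SAP body** (SAP 2.5.3, footnote 1): "Beta-blocker target dose is defined as participants who receive Carvedilol equivalent total daily dose of 50 mg".
- **On-target rule** (SAP Appendix 1, item 5(b)): "If VISITN =50 and Carvedilol equivalent dose = 50 mg then on target dose=1 (yes", followed by "else if Carvedilol equivalent dose is not missing on target dose=0(no".
- **Half-of-target rule** (item 5(c)): "If Carvedilol equivalent dose is at least 25 mg then on 50% target dose=1", followed by "else if Carvedilol equivalent dose is not missing on 50% target dose =0". SAP 9.3 item 1 also describes this component as a threshold.
- **Beta-blocker use** (item 5(a)) is a separate yes/no variable: "BB use at 180 days = CM.CMBB=1 (where VISITID=50". Rules (b) and (c) do not refer to it.
- **Default denominator** (SAP 13.2): "Percentages are calculated out of non-missing values unless stated otherwise".
- **Contrast with ivabradine** (SAP Appendix 1, item 1): "Missing doses will be imputed to 0". There is no matching line for beta-blocker dose.
- **Missing visits** (SAP 13.5): a general sentence treats outcomes of participants without day-180 data as failures. It does not say which endpoints it covers.

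**The concern.** A target dose in an implementation endpoint is normally a level to be reached, and 5(c) shows that the SAP writes a threshold when it means one. Under an equality, a participant above 50 mg becomes a failure on target dose while counting as a success on half of target. The carvedilol-equivalent dose is also a converted quantity whose conversion factors are not given. A nominal target dose that converts to a value slightly off 50 would fail as well.

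At stake is one component of the beta-blocker implementation endpoint. The reported share on target would be too low by the share of participants above 50 mg. If that share differed between arms, the comparison would be distorted.

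The missing-dose handling raises a second question about who is in the denominator. Protocol 3.2, criterion 4, admits patients who cannot take a beta-blocker, and discontinuation is itself an endpoint. Some participants may therefore be off the drug at day 180.

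**Working it through.** The plan states no expected rate or power for this endpoint, so there is no figure of its own to reproduce. The check applies the rules literally and then uses simple proportions.

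**Step 1. Rules applied to a grid of doses (mg carvedilol-equivalent).**

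| Day-180 dose | 5(b) as written | 5(c) as written | 5(b) with 50 or more = 1, off drug = 0 |
|---|---|---|---|
| blank, off drug | no value | no value | 0 |
| 0 | 0 | 0 | 0 |
| 12.5 | 0 | 0 | 0 |
| 25 | 0 | 1 | 0 |
| 37.5 | 0 | 1 | 0 |
| 50 | 1 | 1 | 1 |
| 62.5 | 0 | 1 | 1 |
| 75 | 0 | 1 | 1 |
| 100 | 0 | 1 | 1 |

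The last three rows are the contradiction: at least half of target, yet not on target. The first row shows that a blank dose drops out of both rules, while a recorded 0 stays in.

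**Step 2. Size of the equality effect.** Inputs: 104 enrolled (SAP 2.3); 104/2 = 52 per arm, assuming an even split; 10 people at exactly 50 mg, assumed; nobody off the drug.

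As written: 10/52 = 19.2%, however many are above 50 mg. With a threshold the share is (10 + a)/52, where a is the number above 50 mg:

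- a = 2: 12/52 = 23.1%
- a = 5: 15/52 = 28.8%
- a = 10: 20/52 = 38.5%

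Each such person moves the arm by 1/52 = 1.9 points.

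**Step 3. Size of the denominator effect, if it exists.** Same 52 and 10, nobody above 50 mg, and m people off the drug with a blank dose. As written the share is 10/(52 − m):

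- m = 5: 10/47 = 21.3%
- m = 10: 10/42 = 23.8%
- m = 15: 10/37 = 27.0%

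Keeping them in as not on target gives 10/52 = 19.2%. If they already have a recorded 0, the as-written rule also gives 19.2% and the effect vanishes.

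**Step 4. Both together.** The two effects oppose each other.

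- a = 5, m = 5: 21.3% as written against 28.8% corrected (too low).
- a = 2, m = 10: 23.8% against 23.1% (nearly cancels).
- a = 2, m = 15: 27.0% against 23.1% (too high).

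The net error in an arm therefore has no fixed sign.

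**The case against.** **Other measures catch what this one misses.** Item 5(a) reports use at day 180, 5(d) reports discontinuation, 5(e) compares the dose change by Wilcoxon test, and SAP 6 summarises doses and reasons for not taking a beta-blocker. A participant at 75 mg counts as a success in 5(c). This stands, and it limits the damage: the equality affects only 5(b). It does not make 5(b) correct.

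**Equality is used elsewhere.** The ivabradine maximum-dose rule in Appendix 1 also uses an equality. There the documents state a ceiling (Protocol Table 1), so no dose should lie above it. No ceiling is stated for carvedilol-equivalent dose, so the parallel fails.

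**Leaving out missing values is a declared convention.** That is true under SAP 13.2. A reader might go further and infer that participants who stop the drug do leave the denominator, so that an arm with more stopping looks better. The documents do not support this. Nowhere do they say whether someone off beta-blocker has a recorded dose of 0 or a blank, and with a 0 the problem disappears. What remains is a gap: no rule is given for this case. The failure sentence in SAP 13.5 does not close it, because it concerns people without day-180 data, not an attendee off the drug with a blank dose. Read broadly, it also conflicts with 5(b) and 5(c), which leave missing doses uncoded.

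**No between-arm bias is shown.** This stands. Distortion of the comparison needs the share above 50 mg, or off the drug with a blank dose, to differ by arm, and nothing in the documents shows that it does.

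**Conclusion.** The on-target rule is wrong as written. Item 5(b) and footnote 1 name 50 mg with no lower bound, 5(c) and SAP 9.3 use a threshold for half of target, and no other section corrects the mismatch. This follows from the text alone.

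The denominator point is conditional: it holds only if participants off beta-blocker at day 180 have a blank dose.

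Neither the size nor the direction of any effect on the arm comparison can be known from the documents. The figures above rest on an assumed even split of 104 and on assumed counts at target, above target and off the drug. The severity is minor. The equality affects one component of a tertiary endpoint, the missing-dose question affects that component and its half-of-target companion, and the primary and secondary endpoints and the sample size are untouched.

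**What to change.** 1. In SAP Appendix 1 item 5(b), code on target = 1 when the carvedilol-equivalent dose is 50 mg or more, and change footnote 1 in SAP 2.5.3 to say at least 50 mg. This is endpoint coding only and implies nothing about how patients should be dosed.
2. State the conversion factors and the rounding rule. A value that converts to just under 50 would still fail a threshold.
3. For 5(b) and 5(c) only, code a participant with CMBB = 0 at day 180 as not meeting the criterion. Do this in the category variables, not in the dose variable, so that the dose-change analysis in 5(e) is unchanged.
4. State whether the failure sentence in SAP 13.5 applies to 5(b) and 5(c) for participants with no day-180 medication record.

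No new data are needed, and the programming is a few lines. The real cost is procedural. Addendum 2 to the SAP shows that the database was already locked and unblinded, so the change should go through the supplement or amendment route in SAP section 1. The corrected result should be labelled as post-lock and shown beside the as-written one.
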